#### **6.5 Pre-specified Subgroup Analysis**

No subgroup analyses are planned.

#### **6.6 Supplementary/ Additional Analyses and Outcomes**

There are no supplementary or additional analyses planned.

#### **6.7 Harms**

This analysis will be based on the main population and will be presented as given in Appendix 2.

#### **6.8 Health Economics and Cost Effectiveness (where applicable)**

There is no health economics and cost effectiveness analysis.

#### **6.9 Meta-analyses (if applicable)**

No meta-analysis is planned.

### **7. VALIDATION OF THE PRIMARY ANALYSIS**

Before the trial starts, code for generating dose decisions will be validated by creating 2 large datasets, one for efficacy and one for toxicity, and comparing results from analysis using standard logistic regression with the trial code. Although results will not be identical due to the differences between frequentist and Bayesian

analyses, with fairly vague priors and a large dataset parameter estimates should be similar. Validation will be stored in the statistical eTMF.

## 8. SPECIFICATION OF STATISTICAL PACKAGES

All analysis will be carried out using appropriate validated statistical software such as STATA, SAS, SPLUS or R. The relevant package and version number will be recorded in the Statistical report.

## APPENDIX: GLOSSARY OF ABBREVIATIONS

SAP	Statistical Analysis Plan
DSMC	Data and Safety Monitoring Committee
TSC	Trial Steering Committee
CI	Chief Investigator
CRF	Case Report Form

## **10. APPENDIX 1 SIMULATION RESULTS AND DOSE DECISION TREE**

This is a separate document which is signed by the trial statistician, senior statistician and CI

## **11. APPENDIX 2 TEMPLATE FOR FIRST DOSE DECISION MEETING**

This is a separate document which is signed by the trial statistician, senior statistician and CI

## **12. APPENDIX 3 TEMPLATE TABLES AND FIGURES FOR FINAL STATISTICAL REPORT**

This is a separate document which is signed by the trial statistician, senior statistician and CI

### 13. APPENDIX 4 DEFINITION OF DLT

Definition of DLT as given in Protocol V3.0, 11th August 2019

All patients who have received at least one dose of enadenotucirev will be evaluable for DLTs.

DLTs are defined as any of the following occurring between the start of trial treatment until the Week 13 visit and by the principal investigator (PI) assessed as possibly, probably or definitely related to enadenotucirev or the interaction between enadenotucirev and radiotherapy and/or capecitabine. Patients who experience a DLT will receive no further trial treatment.

Dose limiting toxicities must be reported within 24 hours of the site becoming aware using the SAE form and scan and email as a PDF attachment to [[contact]](mailto:[contact]) and send an email notification to [[contact]](mailto:[contact]).

DLTs will be defined as per NCI CTCAE v4.03, except for proteinuria, and include:

**Renal:**

- Development of proteinuria, 2+ as measured by urinalysis and confirmed with an albumin/creatinine ratio of  $>3\text{g}/\text{mmol}$ , following administration of enadenotucirev, shall be classified as a DLT. No further doses of enadenotucirev will be administered to that patient.

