**and**
  - Urine dipstick for proteinuria at screening and baseline negative or trace. Patients may be included with results of 1+ if they have a spot urinary albumin creatinine ratio (ACR) of either:
    - (i)  $\leq 3$  mg/mmol **or**
    - (ii)  $>3$  mg/mmol with a 24 hour urinary protein  $<1.0$  g/24hours  

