#### 5.3.1 Evaluation schedule A

**Pre- Dose – the following assessments can be completed within 72 hours prior to the dose. Vital signs to be completed on day of dosing**

- Adverse events and DLTs since the previous assessment
- New or changes to existing medications
- Physical examination of major body systems
- Weight
- ECOG performance status
- Local laboratory assessments:
  - Urine dipstick – if 2+ or greater proteinuria enadenotucirev dosing should be interrupted pending completion of 24 hour urine collection to exclude significant proteinuria, see further guidance in section 9.3.

- Routine blood samples
  - Haematology – Hb, white blood cells (WBC) with differential count (neutrophils and lymphocytes) and platelets
  - Biochemistry – sodium, potassium, calcium, phosphate, urea, creatinine, total protein, albumin, bilirubin, alkaline phosphatase (alk phos), AST and/or ALT and LDH
  - Coagulation screen (aPTT and INR)

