#### **Renal:**

- Development of proteinuria, 2+ as measured by urinalysis and confirmed with an albumin/creatinine ratio of  $>3\text{g}/\text{mmol}$  with a 24-hour urinary protein  $\geq 1\text{g}/24\text{h}$  or if there is a decline in eGFR (where a decline in eGFR is defined as eGFR  $<60\text{ml}/\text{min}/1.73\text{m}^2$  or a drop in eGFR by 20% from screening, baseline or previous visit), following administration of enadenotucirev, shall be classified as a DLT. No further doses of enadenotucirev will be administered to that patient.

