**Renal injury:** Three patients out of 123 patients (2.4%) have developed significant renal impairment while receiving enadenotucirev. Whilst no confirmed pathophysiology has been identified it is felt to be due to vascular leakage due to cytokine release. Proteinuria of 2+ on a urine dipstick should therefore be further investigated, due to the potential risk of serious renal injury, with 24 hour urine collection for protein/creatinine ratio. If preferable locally, a urine protein- to-creatinine ratio or urine albumin – to – creatinine ratio are also acceptable in lieu of a 24 hour collection test. Additional blood tests should also be up to date including a serum albumin and serum creatinine. A consultation with nephrology is advised for specialist input. Specifically, early specialist intervention for investigation and treatment if decline in renal function is detected will include:

1. Full renal work-up, including examination of urine sediment, discussion with renal team and then commence high dose corticosteroids and then, if further decline in renal function;
2. Renal biopsy, followed by plasmapheresis should be considered with close involvement of the renal team.

No enadenotucirev is to be administered after the development of proteinuria as this constitutes a DLT.

Refer to section 8.5 for guidance on dose modification/ interruption due to toxicity.

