#### 14.4 Summary of trial safety reporting requirements

Event	DLT	SAE	AE/SAE	AE/SAE
AE/SAE defined as Dose limiting toxicity (DLT) defined as per NCI CTCAE v4.03		Email reporting form within 24 hours	Report in AE CRF	Non reportable
Absolute neutrophil count (ANC) $<0.5 \times 10^9/L$ for $\geq 7$ days	X	X	X	
Febrile Neutropenia (ANC $<1000/mm^3$ with a single temperature of $>38.3$ degrees C or a sustained temperature of $\geq 38$ degrees C for more than one hour.)	X	X	X	
Infection (documented clinically or microbiologically) with Grade 3 or 4 neutropenia (absolute neutrophil count $<1.0 \times 10^9/L$ )	X	X	X	
Thrombocytopenia grade 3 (Platelet count $< 50 \times 10^9/L$ ) in the presence of bleeding or requiring platelet transfusion	X	X	X	
Platelets $<25 \times 10^9/L$ (Grade $\geq 4$ )	X	X	X	
Clinically significant bleeding attributed to grade 3 thrombocytopenia or requiring platelet transfusion or other $\geq 3$ grade clotting disorder or occurring concurrently with Grade 2 or 3 aPTT prolongation, unless there is a clear explanation for the event, such as tumour-related bleeding in the presence of Lupus Anticoagulant	X	X	X	
Clotting event (i.e. deep vein thrombosis [DVT], pulmonary embolism [PE]) occurring concurrently with Grade 2 or 3 aPTT prolongation	X	X	X	
Grade $\geq 3$ diarrhoea for more than 3 consecutive days during within 2 weeks of starting radiotherapy	X	X	X	
Grade $\geq 3$ pneumonitis	X	X	X	
Grade $\geq 3$ cytokine release syndrome	X	X	X	
A concurrent elevation of ALT or AST $>3 \times ULN$ and total bilirubin $>2 \times ULN$ in whom there is no evidence of biliary obstruction or other causes that can reasonably explain the concurrent elevation	X	X	X	
Grade $\geq 3$ nausea or vomiting not controlled by optimal outpatient anti-emetic treatment	X	X	X	
Grade $\geq 3$ diarrhoea despite optimal outpatient anti-diarrhoeal medication use	X	X	X	
Other grade $\geq 3$ effects thought to be directly treatment related to the combination of enadenotucirev with radiotherapy or chemotherapy	X	X	X	
Missing 3 consecutive fractions of radiotherapy, related to enadenotucirev, as judged by the investigator	X	X	X	
Any toxicity causing a delay of radiotherapy completion by greater than one week	X	X	X	
Missing 2 consecutive doses of enadenotucirev due to toxicity	X	X	X	
Death due to drug related complications	X	X	X	

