# 6. ANALYSIS

## 6.1 Outcome Definitions

Primary outcome:

- *Safety*: Binary toxicity measure defined by the occurrence of a DLT or not. This is recorded during the 13 weeks of follow-up after starting treatment. The definition of a DLT is given Appendix 4.
- *Efficacy*: MRI tumour regression grade. This is a 5 point scale that is coded as a binary variable, with scores of 1 or 2 defining a responder and scores of 3, 4 or 5 a non-responder. It is measured at 13 weeks. Patients who did not have the evaluation, or who withdrew or died prior to evaluation will be treated as non-responders. During the trial, for dose-escalation decisions a patient who has not yet reached this time point will not be included in analysis at this decision point. See Appendix 5 for the definition of MRI tumour regression grade

See Section 6.2.1 Primary analysis for definition of the optimal dose.

For dose-escalation interim analyses the safety and efficacy data is taken from the patient status update CRF. For the final determination of the MTD at the end of the trial, the safety outcome will be taken from the *BW135\_DLT\_Assessment* and *BW166\_Adverse\_Events* CRFs and the efficacy outcome taken from the *BW156\_Week13\_Pelvic\_MRI* CRF.

Secondary outcomes:

- Treatment tolerance. This is the amount of capecitabine and radiotherapy received, coded as completing at least 80% of the intended capecitabine dose and at least 20 fractions of radiotherapy. Measured at week 9. Compliance is taken from the *BW150\_Capecitabine* and *BW145\_Radiotherapy* CRF.
- MRI tumour regression grade. See definition for primary outcome, but here it will not be dichotomised. MRI tumour regression grade is taken from the *BW156\_Week13\_Pelvic\_MRI* CRF.
- Pathological complete response. This variable relates to the resected tumour so will only be observed for patients undergoing surgery. It is measured on a 4 point scale, with a score of 1 denoting pathological complete response, and scores 2:4 denoting no pathological complete response. Pathological complete response is taken from the *BW156\_Week13\_Pelvic\_MRI* CRF.
- Neoadjuvant Rectal (NAR) score. This score ranges from 0-100 with a higher score equating to a worse prognosis. It is a derived outcome which components measured on the resected tumour and at initial tumour staging. Therefore, this will only be observed for patients undergoing surgery. It is defined as

- $NAR = \frac{[5pN - 3(cT - pT) + 12]^2}{9.61}$ , where

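### SAP Appendix 4 defines the primary safety outcome with a renal DLT that lacks two limbs of protocol 9.1, and both texts print g/mmol where mg/mmol is meant

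*SAP*

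**What the plan says.** SAP 6.1 makes the primary safety outcome a binary DLT indicator and says: "The definition of a DLT is given Appendix 4". Appendix 4 is labelled as taken from Protocol V3.0. Its renal item is "Development of proteinuria, 2+ as measured by urinalysis and confirmed with an albumin/creatinine ratio of" more than 3 g/mmol after enadenotucirev, with no further condition.

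Protocol 9.1 starts the same way, with the same printed unit. It then adds 24-hour urinary protein of at least 1 g, "or if there is a decline in eGFR (where a decline in eGFR is defined as eGFR" below 60 or a 20% fall from screening, baseline or the previous visit.

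Protocol 4.1 uses the same ratio for eligibility, but in different units. A patient with 1+ on dipstick may enter with a ratio up to 3 mg/mmol, or above 3 "mg/mmol with a 24 hour urinary protein" below 1.0 g.

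Two other protocol sections bear on the point. Section 5.3.1 says that at 2+ or more "enadenotucirev dosing should be interrupted pending completion of 24 hour urine collection to exclude significant proteinuria". The renal paragraph of 9.3 says that spot ratios "are also acceptable in lieu of a 24 hour collection test", and ends: "No enadenotucirev is to be administered after the development of proteinuria as this constitutes a DLT".

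**The concern.** The toxicity model takes one yes/no DLT value per patient, and the dose rule acts on a handful of patients per schedule. Renal harm is a recognised risk of this agent. Protocol 9.3 reports significant renal impairment in 3 of 123 patients (2.4%). Protocol 9.2 lists treatment-related proteinuria of any severity in 20% at 3x10^12 vp and 0% at 1x10^12 vp.

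If the SAP and the protocol define the renal DLT differently, the same patient can count as a DLT under one and not under the other. The SAP does not say which text governs the final analysis. A threshold printed 1000 times too high also makes the confirmatory ratio unusable if anyone applies it as written.

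**Working it through.** **Step 1. The two renal items side by side**

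| Element | SAP Appendix 4 | Protocol 9.1 |
|---|---|---|
| Dipstick | 2+ | 2+ |
| Albumin/creatinine ratio, as printed | >3 g/mmol | >3 g/mmol |
| 24-hour protein | absent | at least 1 g |
| eGFR below 60, or 20% fall | absent | present, joined by *or* |

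The sentence in 9.1 can be read in two ways: eGFR decline is a DLT alone, or it is a second way to confirm 2+ proteinuria. Appendix 4 lacks it on either reading.

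Other items in Appendix 4 differ as well. Febrile neutropenia needs a temperature above 38.5 C, where 9.1 has a single reading above 38.3 C or a sustained 38 C. The missed-dose item says toxicity, where 9.1 says enadenotucirev toxicity. The pattern suggests an older copy.

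**Step 2. The unit**

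Assumed urinary creatinine: 5 to 20 mmol/day (not in the documents). Albumin per day = ratio x creatinine per day.

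- As printed: 3 g/mmol x 5 to 20 = 15 to 60 g/day.
- As in 4.1: 3 mg/mmol x 5 to 20 = 15 to 60 mg/day.
- The 1 g/24h limit as a ratio: 1000 mg / (20 to 5 mmol) = 50 to 200 mg/mmol.

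In mg/mmol, the ratio is a low screen and the 1 g limit a higher bar, as in 4.1. In g/mmol, the ratio alone implies at least 15 g a day, so the 1 g limit in 9.1 could never exclude anyone.

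**Step 3. Patients on whom the renal items disagree or fail**

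| Patient | Unit | Appendix 4 renal item | 9.1 renal item |
|---|---|---|---|
| 2+, ratio >3 mg/mmol, 24-hour protein <1 g, stable eGFR | mg | DLT | not a DLT |
| eGFR falls 20%, no proteinuria | either | not a DLT | DLT only if the limb stands alone |
| 2+, 24-hour protein 2 g, stable eGFR | as printed | not met | not met |

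For the third patient, even if all the protein were albumin, the ratio is 2000/20 to 2000/5 = 100 to 400 mg/mmol, far below 3000.

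**Step 4. What other DLT items already catch**

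Both texts also count related non-haematological toxicity of grade 3 or higher, two consecutive enadenotucirev doses missed for toxicity, and discontinuation for definitely attributable toxicity of any grade. The third patient gets no more enadenotucirev under 9.3. If two or more doses remain, the missed-dose item makes that patient a DLT under both texts. What remains is lower-grade events where dosing resumes, or where fewer than two doses are left, and the discontinuation item is not met.

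**Step 5. What one reclassified DLT can do**

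Model from SAP 6.2.1: logit p = log(alpha) + beta log(x/6), x = 1, 2, 4, 6; log(alpha) ~ N(log(0.3/0.7), 1.44); log(beta) ~ N(-0.1, 0.25). All patients have full weight. The recommended schedule has the highest P(0.2 < p < 0.35) among those with P(p > 0.35) < 0.35. The integral was split exactly at the cut-points.

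Data: 2 patients each on schedules 1 and 2 with no DLT, n3 on schedule 3, none on schedule 4.

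| n3 | 0 DLTs | 1 | 2 | 3 |
|---|---|---|---|---|
| 2 | 4 | 3 | 2 | - |
| 3 | 4 | 3 | 2 | 2 |
| 4 | 4 | 4 | 3 | 2 |
| 5 | 4 | 4 | 3 | 2 |
| 6 | 4 | 4 | 3 | 2 |
| 7 | 4 | 4 | 3 | 3 |
| 8 | 4 | 4 | 4 | 3 |

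Of the 20 one-DLT steps, 12 change the recommendation. With n3 from 3 to 8, the step 0 to 1 changes it in 1 of 6, 1 to 2 in 5 of 6, and 2 to 3 in 4 of 6; both steps at n3 = 2 change it (1 + 5 + 4 + 2 = 12). The entry for n3 = 3 with one DLT is on the boundary: P(p > 0.35) at schedule 4 is 0.3503, just over the limit, so schedule 3. A coarse grid can fall on the other side.

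Examples, written as patients on schedules 1/2/3:

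- 2/2/5, 1 against 2 DLTs on schedule 3: P(p > 0.35) at schedule 4 is 0.24 against 0.49, so schedule 4 against 3.
- 2/2/6, 2 against 3 DLTs on schedule 3: P(p > 0.35) at schedule 3 is 0.20 against 0.42, so schedule 3 against 2.

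With patients on schedule 4 the picture is mixed. For 2/2/6/20 with 1 DLT on schedule 3, 7 against 8 DLTs on schedule 4 gives 0.32 against 0.47, so schedule 4 against 3. For 2/2/2/8 and for 3/3/6/6, with 1 against 2 DLTs on schedule 4 and none elsewhere, schedule 4 stays.

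**The case against.** The strongest reply is that Appendix 4 may never touch the data. Investigators assess DLTs under the protocol, suspected DLTs go to the Chief Investigator and the TMG, and SAP 6.1 reads the final outcome from the DLT assessment and adverse event CRFs. Nothing tells the statistician to reclassify patients from Appendix 4. This stands, and it limits the practical effect. It does not settle which definition governs, because the SAP names Appendix 4 as the definition.

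The unit is plainly a slip, since 4.1 shows what was meant. That is likely, but it sits in a decision threshold in both DLT texts.

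The sensitivity in Step 5 would hold for any DLT item, and some of its states are unlikely paths: the model already recommends schedule 4 after 0 of 2 on schedule 3. That also stands. A reader might take 12 of 20 as the chance that the mismatch alters the dose. It is not: the documents do not say how often the texts would disagree, and a lower choice by the efficacy model can hide a change.

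A reader might also infer that 9.3 sets a third DLT definition, or that 14.4 classes proteinuria as not dose-limiting. Section 9.3 is management guidance that follows a work-up of 2+ proteinuria. Section 14.4 is a reporting summary whose DLT-marked rows include any unlisted grade 3 or higher event and any event leading to withdrawal. Both are matters of alignment.

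**Conclusion.** The point holds as a conflict of wording in the definition of a primary outcome, and it should be corrected. Certain from the text: Appendix 4 lacks the 24-hour-protein and eGFR limbs of 9.1, and the printed ratio limit in both is 1000 times the eligibility figure. The consequence is confined to lower-grade renal events that the three shared items in Step 4 do not catch. Its frequency is unknown, and no probability of a wrong dose is claimed.

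A reader might infer that the final dose will be chosen on a different definition from the one used at the sites. The documents do not support that, because the recorded DLTs come from investigators working to the protocol.

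The conclusion rests on three assumptions. Creatinine output of 5 to 20 mmol/day is used only to size the unit error. The refits use full weights and the model probability itself in the likelihood. That Appendix 4 is an older copy is inferred from its V3.0 label and its other differing items, because the version of the supplied protocol is not shown in the text reviewed. The mismatch exists whatever its cause.

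**What to change.** - Correct g/mmol to mg/mmol in the renal items of protocol 9.1 and SAP Appendix 4.
- Replace Appendix 4 with the current 9.1 text, including the febrile-neutropenia and missed-dose items. Correct the version label, which dates Protocol V3.0 to August 2019 where SAP 1.2 and Appendix 5 say August 2020.
- State in SAP 6.1 that the current protocol definition governs the final analysis.
- State in 9.1 whether eGFR decline counts alone or only together with 2+ proteinuria.
- Align the last sentence on renal injury in 9.3 with 9.1: confirmed proteinuria is the DLT, and say whether a spot ratio is enough to confirm it.
- Optionally, add a named renal row to the DLT section of 14.4.

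The cost is a wording amendment to both documents and short clinical decisions on the eGFR limb, confirmation of proteinuria and the spot ratio. No analysis is added. No assessment is added either, unless the 24-hour collection becomes mandatory at sites that now use a spot ratio.

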**Acute hematologic toxicity:**

- Infection (documented clinically or microbiologically) with grade 3 or 4 neutropenia (absolute neutrophil count (ANC)  $<1.0 \times 10^9/\text{L}$ )
- Neutropenia grade 4 (ANC  $< 0.5 \times 10^9/\text{L}$ ) lasting for  $> 6$  days
- Febrile neutropenia grade 4 (fever of unknown origin without clinically or microbiologically documented infection) (ANC  $<1.0 \times 10^9/\text{L}$ , fever  $>38.5^\circ\text{C}$ )
- Thrombocytopenia grade 3 (Platelet count  $< 50 \times 10^9/\text{L}$ ) in the presence of bleeding or requiring platelet transfusion
- Thrombocytopenia grade  $\geq 4$  (Platelet count  $< 25 \times 10^9/\text{L}$ )
- Anemia grade 3 in the presence of blood transfusion dependency as judged by the PI
- Anemia grade  $\geq 4$
- Clinically significant bleeding attributed to grade 3 thrombocytopenia or requiring platelet transfusion or other grade  $\geq 3$  clotting disorder or occurring concurrently with Grade 2 or 3 aPTT prolongation, unless there is a clear explanation for the event, such as tumour-related bleeding in the presence of Lupus Anticoagulant.
- Any other grade  $\geq 3$  non-hematological toxicity with the exception of: activated partial thromboplastin time (aPTT) prolongation
- Clotting event (i.e. deep vein thrombosis [DVT], pulmonary embolism [PE]) occurring concurrently with Grade 2 or 3 aPTT prolongation

**Acute non-hematologic toxicity:**

- Any documented  $\geq$  grade 4 non-hematologic toxicity in the presence of maximal support/active management
- Grade  $\geq 3$  cystitis or radiation dermatitis onset within 2 weeks of starting radiotherapy or lasting more than 2 weeks after the end of radiotherapy.
- Grade  $\geq 3$  proctitis or diarrhea onset within 2 weeks of starting radiotherapy
- Grade  $\geq 3$  nausea or vomiting not controlled by optimal outpatient anti-emetic treatment
- Grade  $\geq 3$  diarrhea despite optimal outpatient anti-diarrheal medication use

- Grade ≥3 hematuria or neuropathic pain
- Other grade 3 ≥ effects thought to be due to the combination of enadenotucirev with radiotherapy
- Missing 2 consecutive doses of enadenotucirev due to toxicity
- An elevation of ALT or AST >5 x ULN lasting 8 days or more
- A concurrent elevation of ALT or AST >3 × ULN and total bilirubin >2 × ULN in whom there is no evidence of biliary obstruction or other causes that can reasonably explain the concurrent elevation
- Death due to drug related complications
- Grade ≥3 cytokine release syndrome

**General:**

- Discontinuation of the active treatment due to toxicity definitely attributable to enadenotucirev, irrespective of the grade of toxicity
- Missing 3 consecutive fractions of radiotherapy, related to enadenotucirev, as judged by the PI
- Any toxicity causing a delay of radiotherapy completion by greater than one week

This is not an exhaustive list. All suspected DLTs should be discussed with the Chief Investigator and the Trial Management Group.

